
analyses that examine FTO gene polymorphisms coupled with certain types of dietary intervention which are then associated with changes in nutritional status, body composition, and various inflammatory and hormonal biomarkers in obese subjects (Razquin et al. 2010; De Luis et al. 2012b; De Luis et al. 2015a; De Luis et al. 2015b; Luglio et al. 2017; Di Renzo et al. 2018; De Luis et al. 2020; Parastouei et al. 2020), however, some things are still unclear and limited. Apart from that, no one has ever linked the FTO gene polymorphism to the Balanced Nutrition Diet intervention which is the reference in Indonesia, as well as its effect on cardiovascular risk.
 
Research purposes:
 
General purpose:
 
Examining the Effect of a Balanced Nutritional Diet on Cardiovascular Risk Factors Among Two Types of FTO rs9939609 Gene in Obese Young Women.
 
Special purpose:
 
 1. Analyze differences in the body composition of obese young women between A allele carriers (AC) and TT allele homozygous (TH) groups after Balanced Nutrition Diet intervention 2. Analyze differences in biomarkers of inflammation related to cardiovascular risk (interleukin (IL-6), high-sensitivity CRP (hs-CRP), and adiponectin (ADP)) of obese young women between A allele carriers (AC) and TT allele homozygous (TH) groups after Balanced Nutrition Diet intervention 
Benefits of research:
 
For research subjects, subjects can find out the allele type of the FTO rs9939609 gene themselves as an illustration of genes related to obesity and that can be used as a basis for precision nutrition interventions and will receive nutritional education about balanced nutrition. For the public, it is hoped that this research can increase knowledge about consumption recommendations, especially to normalize nutritional status and reduce the risk of cardiovascular disease by improving health status, especially for young adult women. For educational institutions, it is hoped that this research will provide new scientific evidence in the field of nutrigenomics regarding the interaction of genes and diet influencing the risk of obesity and cardiovascular disease. For the government, it is hoped that it can become a reference for making a policy to reduce obesity cases in Indonesia.
 
Number of Research Subjects:
 
This research uses a hypothesis testing formula for 2 independent samples based on Sastroasmoro & Ismael (2014):
 $n_1 = n_2 = 2 \left[\frac{(Z_{\alpha} + Z_{\beta})S}{X_1 - X_2} \right]^2$ 
The results of calculations using data from previous research (De Luis et al. 2015b) resulted in 7 people. This study used 4 groups, namely 2 control groups and 2 intervention groups, adding an anticipated dropout of 50%, the total number of subjects was at least 44 people or 11 people per group.
 
Information:
 
n = minimum number of subjects
 
Z_{α} = type I error (1.96)
 
Z_{β} = type II error (1.28; power 90)
 
S = standard deviation of the two groups
 
$X_1 - X_2$ = desired clinical difference (difference in weight between Allele T and Allele A)
 
Research by De Luis et al. (2015b) is a consideration for the expected weight loss of subjects in this study, namely assuming a weight loss of ± 1 kg in A allele carriers and ± 0.35 kg in homozygous T subjects after 1 month of intervention with the balanced nutritional diet provided.
 
How to Choose Research Subjects

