--	---

	
the FTO SNP rs9939609 was associated with changes in REE adjusted for fat mass and lean mass, with the AA allele showing a decrease compared to TT.
 
Several studies have been conducted looking at the relationship between the FTO rs9939609 genotype and interleukin-6 (IL-6) levels, but only a few have shown real differences (de Luis et al. 2012b; Zimmermann et al. 2011; de Luis et al. 2016; Magno et al. 2018; Hosseini et al. 2011). Studies have also been conducted that there is an association of FTO rs9939609 with higher levels of C reactive protein (CRP) (Fisher et al. 2009; Sun et al. 2010; Lappalainen et al. 2011; Tupikowska-Marzec et al. 2019). However, other studies show contradictions (Zimmermann et al. 2011).
 
Research by Mehrdad et al. (2020a) showed that subjects with A allele carriers (AA and AT) had lower adiponectin levels than wild-type subjects (homozygous TT) with homozygous AA allele types having the lowest values although not significantly different. Several other studies also show the same thing in both obese and other types of adult subjects (Saucedo et al. 2017; Isgin-Atici et al. 2021). However, research by de Luis et al. (2016) and Duicu et al. (2016) showed a contrast, namely that adiponectin levels were lower in the TT genotype group compared to the AA genotype group. Based on what has been explained above, several outcome indicators that will be analyzed are waist-hip circumference, mass and total fat percentage &visceral, interleukin-6 levels, hs-CRP levels, and adiponectin levels.
 
Statistical analysis
 
The data obtained were tested statistically using SPSS statistical software for Windows (IBM version 26.0, SPSS Inc., Chicago, Ill., USA). The normality of variable distribution was verified with the Shapiro-Wilk test. Analysis of Variance (ANOVA) was used for all baseline data. Paired samples t-test was used to see changes in calorie intake, macronutrients, BW, BMI, waist circumference, hip circumference, waist-hip ratio, RM, percent total fat, visceral fat, subcutaneous fat, skeletal muscle, IL-6, hs-CRP, and adiponectin between before and after intervention. Data are presented as mean \pm SD and P < 0.05 was considered statistically significant.
 
c) Planned interim analysis: There is no interim analysis in this study.
 
d) Clinical trial termination procedures: Referring to the guidelines for good clinical trials in Indonesia (POM RI 2016), clinical trials are terminated if clinical trial safety problems occur, such as serious undesirable events and serious side effects of the test product. The principal investigator will report the KTDS to the ethics committee no later than 3 days after the incident is discovered. The possibility of KTDS that could occur in this study is that the patient requires hospital treatment as a result of the intervention process.
 
e) Estimated research time required for one subject per procedure: \pm4 weeks
 
f) Ethical issues (state your opinion about the ethical issues this research may encounter):
 
 • Respect for person (respect for human dignity): Subjects in this study took part based on their own conscious choice, there was no element of coercion. Subjects have the right to be protected, including that all Subject data will be kept confidential. • Beneficence(beneficial) Non-maleficence (not harmful): This research optimizes benefits and minimizes harm to subjects. The results of the research will be useful for society. The research design has been made as clear as possible. Researchers have competencies that are appropriate to the research topic to be conducted. • Justice(justice): Subjects are treated the same/or there is no differentiation between subjects.

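### No between-group test after the intervention: outcomes get only a before-after paired t-test, so neither the genotype comparison nor the randomised diet effect is tested

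*Combined protocol and SAP*

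**What the plan says.** The statistical analysis paragraph in section B.9(b) names three procedures:

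- a Shapiro-Wilk check of normality;
- for baseline, "Analysis of Variance (ANOVA) was used for all baseline data";
- for outcomes, "Paired samples t-test was used to see changes in calorie intake, macronutrients, BW, BMI, waist circumference" and further variables, ending with "IL-6, hs-CRP, and adiponectin between before and after intervention".

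The significance level is 0.05. The paragraph does not say whether the paired test is run within each of the four groups or on pooled subjects, or how paired results would be compared across groups.

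Other parts of the protocol ask for comparisons between groups:

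- General purpose (B.1): "Examining the Effect of a Balanced Nutritional Diet on Cardiovascular Risk Factors Among Two Types of FTO rs9939609 Gene in Obese Young Women".
- First special purpose (B.1): "Analyze differences in the body composition of obese young women between A allele carriers (AC) and TT allele homozygous (TH) groups", following the diet.
- Second special purpose (B.1): "Analyze differences in biomarkers of inflammation related to cardiovascular risk", again A carriers (AC) versus TT homozygotes (TH) after the diet.
- Sample size (B.1): "This research uses a hypothesis testing formula for 2 independent samples", with the difference in weight between alleles as the target.
- Allocation (B.9(a)): 1:1 diet to control within each genotype block. This gives DAC and DTH (diet) and CAC and CTH (control). All four groups receive nutrition education.

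**The concern.** The design and objectives are about differences between groups, but the listed tests look only at change over time. A paired change cannot separate the diet from the passage of time, from the education given to everyone, or from possible regression to the mean (entry requires body fat above 35%). Removing those explanations is the purpose of the control groups, yet no test contrasts them with the diet groups after the intervention.

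A significant paired change in a diet group would therefore not show that the diet worked. A significant change in one genotype and a non-significant change in the other would not show that the genotypes differ. Because the plan gives no rule for comparing groups, any such comparison would be chosen after the data are seen.

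**Working it through.** **1. Match each question to a planned test.**

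| Question in the protocol | Contrast needed | Planned test |
|---|---|---|
| Special purposes 1 and 2 | DAC - DTH after the diet | none |
| Effect of the diet | DAC - CAC and DTH - CTH | none |
| Diet effect across the two FTO types | (DAC - CAC) - (DTH - CTH) | none |
| Groups at baseline | four groups before treatment | ANOVA |
| Change over time | after - before | paired t-test |

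Whether the paired test is run per group or pooled, none of the first three rows is answered. This finding needs no arithmetic.

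**2. Reproduce the sample size and recover S.** The formula is n = 2[(1.96 + 1.28)S / 0.65]², with 0.65 = 1 - 0.35 kg. S is not printed, so the 7 per group cannot be recomputed directly. Solving for S gives S = 0.65·√(n/2)/3.24:

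- n = 6: 0.65 × 1.732/3.24 = 0.3475 kg
- n = 7: 0.65 × 1.871/3.24 = 0.3753 kg

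So 7, if rounded up, implies S of about 0.347-0.375 kg, taken here as the SD of weight change. An assumed wider value of 0.6 kg is shown as well. The total reproduces: 7 × 1.5 = 10.5, rounded up to 11, times 4 = 44.

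**3. What a paired test shows when the diet adds nothing.** Assume every group, controls included, loses 0.35 kg. Power of a paired t-test comes from the noncentral t with df = n - 1 and noncentrality 0.35·√n/S, two-sided 5%. For n = 7 and S = 0.3753 the noncentrality is 0.35 × 2.646/0.3753 = 2.47 and the power is 0.543.

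| | S = 0.375 | S = 0.347 | S = 0.6 |
|---|---|---|---|
| Paired test significant, 7 completers | 54% | 61% | 26% |
| Paired test significant, 11 completers | 80% | 85% | 42% |
| Exactly one of two significant, 7 completers | 50% | 48% | 38% |
| Exactly one of two significant, 11 completers | 32% | 25% | 49% |

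The last two rows are 2p(1 - p), for two genotypes with the same true loss; for example 2 × 0.543 × 0.457 = 0.496. A direct diet-control or DAC - DTH test would be significant 5% of the time. A simulation of 40,000 trials agreed, with direct tests at 4.8-5.3%.

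**4. What direct contrasts could detect.** These use unadjusted change, pooled error with df = 4n - 4, SE = S·√(2/n) for a two-group contrast and S·√(4/n) for the interaction. Ranges are for S from 0.375 down to 0.347; S = 0.6 is in brackets.

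| Completers per group | DAC - DTH, 0.65 kg | Interaction, 0.65 kg | DTH - CTH, 0.35 kg |
|---|---|---|---|
| 7 | 87-92% (49%) | 59-66% (28%) | 39-44% (18%) |
| 11 | 98-99% (70%) | 80-86% (42%) | 57-64% (27%) |

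With 7 completers t(24) = 2.064. The 95% CI half-width for a two-group contrast is 2.064 × S × √(2/7), or 0.38-0.41 kg (0.66 kg at S = 0.6). For the interaction it is 2.064 × S × √(4/7), or 0.54-0.59 kg (0.94 kg).

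**The case against.** The omission itself is hard to dispute, but several points on the other side have force.

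- **Controls may still be analysed.** The paired test is not limited to the diet groups, so CAC and CTH may get a before-after test too. This is right. The defect is that no test contrasts the groups, not that control data go unused.
- **The illustration is built on assumptions.** S is back-solved, 0.6 kg is assumed, and the 0.35 kg loss is the plan's figure for TT subjects on the diet, applied here to everyone. The one-of-two figures also suppose that readers would infer a difference from unequal significance, which the plan does not say. This stands, so the figures show the scale of the risk and are not evidence for the omission.
- **The power figures may be too kind.** A literal 50% loss from 11 per group leaves 5-6 completers. Power is then about 73-87% for DAC - DTH, 44-59% for the interaction and 28-38% for DTH - CTH at S 0.347-0.375. This belongs in the stated downside.
- **ANCOVA is one choice among several.** A between-group test of change would also cure the omission. For the non-randomised DAC - DTH contrast, ANCOVA and change scores can disagree if genotypes differ at baseline, and B.9(b) cites evidence that A carriers weigh more. This matters for how that contrast is reported.
- **Special purposes are loosely worded.** They do not use the label DAC - DTH or say whether endline or change is meant. That is a further reason to write the contrast down.

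**Conclusion.** The concern holds and must be fixed. The analysis as written answers neither special purpose and provides no controlled estimate of the diet effect, although the data for both are collected. That conclusion rests on the text alone. The size of the risk depends on an unprinted SD. Over S from 0.347 to 0.6 kg and a 0.35 kg loss in every group, a diet group's paired test would be significant in 26-61% of trials with 7 completers and 42-85% with 11, with no diet effect at all. The matching figure for a direct test is 5%. Low power for some contrasts is a reason to report intervals; it does not justify leaving the comparisons out.

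**What to change.** Make a between-group model the inferential analysis and keep paired changes as description. A suitable form is one linear model per outcome, with endline as the response and baseline value, diet, genotype and diet × genotype as terms. From it report, with 95% confidence intervals:

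- DAC - CAC and DTH - CTH, the randomised diet effects;
- DAC - DTH, for the special purposes, labelled non-randomised, with the change-score result alongside because the two can differ when genotypes are unequal at baseline;
- the interaction, interpreted by its interval.

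If endline data have already been analysed, label this analysis as added afterwards.

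The cost is plan wording and one SPSS model per outcome; no new measurements are needed. The plan should state the limited power and precision shown above, including the case of 5-6 completers. Baseline adjustment could improve these figures, but the documents give no before-after correlation from which to say by how much.

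Separately, the sizing uses weight, while the indicator list ("several outcome indicators that will be analyzed are waist-hip circumference, mass and total fat percentage", then visceral fat and the three biomarkers) omits it, although body weight is among the paired-test variables. The two should be reconciled when a primary outcome is named.

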	
If necessary, collection of additional or incomplete data is carried out online/by telephone or at the subject's place if the subject permits.
 
Blood specimen testing was carried out at the Molecular Genetics Laboratory, Faculty of Medicine, Padjajaran University.
								
8.	Research Time Plan: ± 4 months	Starting: November 2023	Completed: February 2024						
9.	Data Collection Time Starting: November 2023 to February 2024								
10.	
Has This Protocol Been Submitted to Another Ethics Commission?
 
 
  Yes	 Accepted	
 
 If yes, attach a photocopy of the document!	
 
  No	
 
			 Yes	 Accepted	If yes, attach a photocopy of the document!		 No	
 Yes	 Accepted								
If yes, attach a photocopy of the document!									
 No									
11.	Allocation and Details of Research Funds (Human Resources, Consumables, etc.):								
	No.	Type of Spending	Component	Fee Required					
	1	Material	ATK	IDR 500,000					
	2	Material	Diet Procurement (20x3x30x45,000)	IDR 81,000,000					
	3	Material	Elisa Kit (IL-6; hs-CRP; adiponectin)	IDR 23,532,000					
	4	Material	DNA isolation kit (40x200,000)	IDR 8,000,000					
	5	Material	Primary (1x400,000)	IDR 400,000					
	6	Material	Primary Design Services (1x150,000)	IDR 150,000					
	7	Material	Subject Reward (40x35,000)	IDR 1,400,000					
	8	Data collection	FGD research preparation (5x105,000)	IDR 525,000					
	9	Data collection	Survey Officer's Honorarium (Screening: 40x8,000)	IDR 320,000					
	10	Data collection	Temporary Blood Glucose Test (40x18,000)	IDR 720,000					
	11	Data collection	Researcher Administration Honoraria	IDR 300,000					
	12	Data collection	Transport subject + officers (43x25,000x2)	IDR 2,150,000					
	13	Data collection	Data collection meetings (5x105,000)	IDR 525,000					
	14	Equipment Rental	Research Equipment (2x350,000)	IDR 700,000					
	15	Specimen Analysis	PCR Gene Amplification (42x100,000)	IDR 4,200,000					

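### The plan anticipates 50% dropout, but its only outcome test uses women with both values, and nothing says women who stop the diet are still measured at day 28

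*Combined protocol and SAP*

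**What the plan says.** All references are to the combined protocol and SAP.

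- **Item B.9(b), Statistical analysis.** After a normality check, the plan names two tests. For baseline: "Analysis of Variance (ANOVA) was used for all baseline data". For outcomes: "Paired samples t-test was used to see changes" in intake, anthropometry, body composition, IL-6, hs-CRP and adiponectin. No analysis set, missing-data method or sensitivity analysis is given.
- **Item B.1, Number of Research Subjects.** The formula gives 7 per group. The plan then reaches 11 per group, 44 in total, by "adding an anticipated dropout of 50" percent. The design difference comes from "assuming a weight loss of ± 1 kg in A allele carriers and ± 0.35 kg in homozygous T subjects".
- **Item B.9(a).** Women are randomised 1:1 to diet or control within each genotype block, which makes four groups. Outcome blood is drawn at baseline and once more after 28 days. No outcome visit in between is described.
- **Data-collection paragraph above item 8 (Research Time Plan).** If needed, "collection of additional or incomplete data is carried out online/by telephone", or at the woman's home with her permission.
- **Item B.10(d).** Discontinuation is discussed only in connection with adverse events.

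**The concern.** A paired t-test needs two values per woman. With a single endline, a woman without a day-28 value contributes nothing to any outcome result. That would matter little at low dropout, but the plan itself expects to lose up to half its sample. The trial is open-label. The diet groups receive three supplied meals a day and the controls receive none, so reasons for leaving may differ by arm and may be related to weight change.

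Two quantities are at stake. One is the before-after change in each group, which is what the plan tests. The other is the difference between A carriers and TT women after the diet, which is the stated objective. Selective loss can bias the first. It can also bias the second if loss, or its relation to weight change, differs between the groups compared.

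**Working it through.** **1. Reproduce the plan's sample size.** The inputs from item B.1 are 1.96, 1.28, a difference of 1 - 0.35 = 0.65 kg, and n = 7. The SD is not stated. Solving n = 2[(1.96 + 1.28)S / 0.65]^2 for S gives:

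- n = 7: S = 0.65 x sqrt(7/2) / 3.24 = 0.375 kg
- n = 6: S = 0.65 x sqrt(6/2) / 3.24 = 0.347 kg

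Rounding up to 7 therefore requires S above 0.347 and at most 0.375 kg. The dropout step is 7 x 1.5 = 10.5, rounded up to 11, and 4 x 11 = 44. This matches the plan.

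**2. How many women enter the test.** At 50% loss, about 22 of 44 remain, or 5 to 6 per group. Eleven per group keeps 7 only if loss is 1 - 7/11 = 36%, which leaves 4 x 7 = 28. Since the plan's arithmetic fits 36% and its wording says 50%, I show both.

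**3. Bias in one group's mean change.** In general, bias = dropout share x (mean change in completers minus mean change in women lost). The documents do not give that gap. I use a normal selection model in which rho is the assumed correlation between a woman's weight loss and her tendency to complete:

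bias = rho x S x phi(z) / (1 - d), where d is the dropout share, z the normal quantile at d, and S = 0.375 kg.

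At d = 0.5, phi(0)/0.5 = 0.798. With rho = 0.5 the bias is 0.5 x 0.375 x 0.798 = 0.150 kg, and 0.150/0.65 = 23%.

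| rho (assumed) | 50% loss: kg (% of 0.65) | 36% loss: kg (% of 0.65) |
|---|---|---|
| 0 | 0 (0%) | 0 (0%) |
| 0.1 | 0.030 (5%) | 0.022 (3%) |
| 0.3 | 0.090 (14%) | 0.066 (10%) |
| 0.5 | 0.150 (23%) | 0.111 (17%) |
| 1.0 (ceiling) | 0.299 (46%) | 0.221 (34%) |

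The percentages are only a scale: 0.65 kg is a between-genotype difference, while the bias here is in one group's before-after mean.

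**4. Limit without the normal assumption.** With a 50/50 split, the variance between completers and women lost is 0.25 x gap^2, which cannot exceed S^2. So the gap is at most 2 x 0.375 = 0.75 kg. The bias is then at most 0.5 x 0.75 = 0.375 kg, or 58% of 0.65.

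**5. Bias in a contrast of two groups.** If the gap is the same in both, bias = (dropout share in one minus dropout share in the other) x gap. Equal shares give zero. For an assumed gap of 0.25 kg, 60% against 40% loss gives 0.20 x 0.25 = 0.05 kg (8% of 0.65), and 70% against 30% gives 0.40 x 0.25 = 0.10 kg (15%).

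**The case against.** **The plan never says completers only.** True: a paired test could be run on imputed values, so the restriction is the consequence of the named test and not a declared policy. But no imputation is mentioned, and with one endline the default is clear.

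**Stopping the diet is not the same as having no endline.** This also stands. A woman who stops the meals but attends on day 28 is in the paired test, so only women without an endline value cause the problem. Giving up supplied meals also cannot explain loss among controls, who receive none. The gap is that no instruction secures the day-28 visit.

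**Incomplete data can be retrieved.** Home collection could reduce the loss. A telephone or online contact cannot supply bioimpedance or blood values, and retrieval is not an analysis rule.

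**A better model would not remove the bias.** Largely right. With two time points, a longitudinal model or imputation assumes that dropout is explained by observed data. It cannot correct selection on a change nobody measured. Retrieval and the sensitivity analysis must therefore lead.

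A reader might infer two stronger claims. The first is that the completer result overstates the effect of the diet. The documents give no reasons for leaving, so the direction is an assumption. The second is that the bias could reach 0.5 x 1.0 = 0.50 kg, or 77% of 0.65, if A carriers who leave lose nothing while completers lose 1 kg. That gap of 1.0 kg exceeds the 0.75 kg maximum allowed by the plan's implied SD, if that SD describes change in all women.

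**Conclusion.** The point holds in limited form and should be acted on. It is certain that the plan's one outcome test, applied as written, leaves out every woman without a day-28 value, at a loss the plan puts at 50% by its wording and 36% by its arithmetic. It is also clear that the available text has no instruction for day-28 measurement after a woman stops the diet.

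The size and direction of any bias are not known. Moderate selection puts the group-mean bias between a few percent and about a quarter of the design difference. It vanishes if dropout is unrelated to weight change, and it cancels in the genotype contrast if loss and gap are equal across groups, though it then remains in each paired change. These figures rest on a back-solved SD read as the SD of weight change, on the normal selection model and on assumed correlations. They cover weight only, since the documents give no SD for the biomarkers.

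**What to change.** In order of importance:

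1. **Secure the endline.** State that stopping the diet does not end outcome collection. Ask every randomised woman who still consents for day-28 anthropometry and blood, at her home if needed, using the route the protocol already allows. Values not collected at the time cannot be recovered.
2. **Analyse as randomised.** Keep all randomised women in their assigned group. Replace the separate paired t-tests with one baseline-adjusted or baseline-constrained model comparing the four groups. The constrained longitudinal form keeps every baseline value; constrain baseline means to be equal between arms within a genotype, not across genotypes, because genotype is not randomised. State that the model assumes dropout is explained by observed data.
3. **Add one sensitivity analysis.** Give diet-arm women without an endline value the control-group change of the same genotype. With few women per group this will be imprecise, so report it alongside the main result.
4. **Report dropout by arm and genotype**, with reasons where known.

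The cost is some rewording, modest extra analysis and extra endline visits. At the planned loss these could involve 16 (44 - 28) to 22 women and need measurement and venous blood, not a call. The resulting estimate may be smaller than the completer estimate.

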	
be conducted using the block randomization method, based on the FTO gene allele. This process will involve two sample randomization blocks: one for A carriers allele and another for T homozygous individuals. Each block will then be randomized and divided into two groups, maintaining a 1:1 ratio between control and dietary intervention. Following randomization, four groups will be formed: two groups receiving the Balanced Nutrition Diet intervention (DAC: A allele carriers + Diet; and DTH: homozygous T allele + Diet), and two control groups (CAC: A allele carriers; and CTH: homozygous T allele). Nutrition education will be provided to all groups. The intervention period will span 4 weeks (28 days), after which a second blood draw will be conducted to gather endline data.
 
The Balanced Nutrition Diet is meticulously designed to supply the body with nutrients in suitable types and quantities, adhering to the principles of food diversity which include variety, balanced proportions, correct amounts, and consistency. Additionally, it emphasizes the "Fill My Plate" guideline, advocating for the consumption of all five food groups daily or at each meal. Portion sizes of the Balanced Nutrition Diet are structured according to the "Balanced Nutrition Tumpeng" model, encompassing 3-4 portions/day of carbohydrates, 2-3 servings/day of fruit, 3-4 servings/day of vegetables, and 2-4 servings/day of side dishes, with restrictions set at 4 tablespoons of sugar, 1 teaspoon of salt, and 5 tablespoons of oil per day, alongside a recommendation of drinking 8 glasses of water daily.
 
During the intervention period, food is provided three times a day - breakfast, lunch, and dinner - following a 28-day menu cycle. The researcher bears the sole responsibility for covering the cost of all food provided to the intervention group during this 28-day period. The Balanced Nutrition Diet offered adheres to specific macronutrient distribution ratios of 45-55% carbohydrates, 15-20% protein, and 20-25% fat, as outlined by Almatsier (2010). Complex carbohydrates, such as whole grains, are prioritized, while protein sources lean towards low-fat options, with half derived from plant-based sources. Monounsaturated and polyunsaturated fats are favored, and organic ingredients are preferred whenever possible.
 
Each meal's composition adheres to the "Fill My Plate" principle, and daily portions follow the "Balanced Nutrition Tumpeng" concept. Specifically, the diet provided by Eat & Fit Catering adheres to certain guidelines, including cooking methods that eschew fire and oil frying in favor of boiling, sautéing, or roasting techniques. Canola oil is the preferred oil, sodium-reduced salt is utilized, and mushroom stock serves as the primary flavouring agent, ensuring both healthfulness and taste. For each subject, energy requirements were calculated according to resting energy expenditure (REE) estimates using Mifflin-St. Jeor Equation (Mifflin et al. 1990). REE is then multiplied by the physical activity level (PAL) according to WHO-FAO that has been obtained.
 
REE (women)= (9.99 x Body Weight) + (6.25 x Height) + (5 x Age) – 161
 
The dietary distribution to subjects occurs three times, facilitated by couriers from the catering party. Should the delivery fall beyond the catering courier's radius, online delivery services will be utilized, with costs borne by the researcher.
 
In contrast, the control group subjects do not adhere to a specific diet regimen. However, they will receive general guidance on healthy eating habits and will be monitored closely. Nonetheless, their energy requirements will still be assessed based on REE and physical activity levels, as previously mentioned.
 
b) Determination of outcome indicators:
 
Evidence shows that compared with TT wild type, the risk allele A FTO rs9939609 showed significantly higher body weight, body mass index, waist circumference, hip circumference, and waist-to-hip ratio (Mangge et al. 2011; Tupikowska-Marzec et al. al. 2019; Mehrdad et al. According to Chrostowska et al. (2013), evidence is growing that the waist-hip circumference ratio is a stronger indicator of cardiovascular disease than body mass index. The meta-analysis of Gholamalizadeh et al. (2020), showed that carriers of the A allele of the FTO rs9939609 polymorphism had a higher fat percentage. The research results of Dorling et al. (2021) showed

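### The aims and sample size concern a difference between FTO genotypes, but the analysis section assigns no test to it: change is tested only before versus after, with no primary outcome

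*Combined protocol and SAP*

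**What the plan says.** **Aims (B.1, Special purpose).** Both specific aims are genotype comparisons after the diet. The first reads "Analyze differences in the body composition of obese young women between A allele carriers (AC) and TT allele homozygous (TH) groups", and the second has the same form for IL-6, hs-CRP and adiponectin.

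**Sample size (B.1, Number of Research Subjects).** The formula is for two independent samples, with z values of 1.96 and 1.28 (90% power). Its denominator is the "desired clinical difference (difference in weight between Allele T and Allele A"). The assumed losses are about 1 kg in A carriers and "0.35 kg in homozygous T subjects after 1 month of intervention with the balanced nutritional diet provided". No number is given for S, the standard deviation.

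**Design (B.9(a)).** Randomisation to diet or control is 1:1 within each genotype, so "four groups will be formed: two groups receiving the Balanced Nutrition Diet intervention" (DAC and DTH) and two control groups (CAC and CTH).

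**Outcome indicators (B.9(b)).** The list is unranked: "several outcome indicators that will be analyzed are waist-hip circumference, mass and total fat percentage", then visceral fat, IL-6, hs-CRP and adiponectin. Body weight is not in it. The word mass there reads as fat mass, because B.10(b) lists it separately from body weight.

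**Statistical analysis (B.9(b)).** After a normality check, "Analysis of Variance (ANOVA) was used for all baseline data". For change, "Paired samples t-test was used to see changes in calorie intake, macronutrients, BW, BMI, waist circumference, hip circumference" and nine further items. The threshold is "P < 0.05 was considered statistically significant". The available text names no primary outcome and no between-group test of change, and does not say whether the paired tests are run within each group or on all participants together.

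**The concern.** Followed as written, the analysis never estimates the quantity that the aims name and the trial was sized to detect. A paired test asks whether a group changed from its own baseline. It does not say whether A carriers changed more than TT homozygotes, or whether diet changed more than control.

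Readers would then be left to set one group's p-value beside another's. One group can fall below 0.05 and the other above it when the two groups do not differ at all, and this would be read as a genotype effect.

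The lack of a named primary outcome adds a second, smaller problem. Many outcomes share one threshold and none is marked as the main result. The 90% power could also be taken to cover the paired tests or the cardiovascular indicators, none of which was sized.

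**Working it through.** **1. The plan's own figure.** 7 per group × 1.5 = 10.5, rounded up to 11; 11 × 4 = 44. This matches the stated total. The 7 cannot be checked, because S has no value.

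**2. The SD implied by 7.** The formula is n = 2[(1.96 + 1.28)S/0.65]², with 0.65 = 1 − 0.35 kg. Solving gives S = (0.65/3.24)√(n/2).
- n = 6 gives S = 0.347 kg.
- n = 7 gives S = 0.375 kg.

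The formula therefore rounds up to 7 only for S between about 0.347 and 0.375 kg. I take S as the SD of weight change.

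**3. Paired tests with no genotype difference.** Suppose both diet groups truly lose 0.35 kg, the plan's own TT figure. Each paired test has non-centrality 0.35√n/S. With p its power (two-sided 0.05, n − 1 degrees of freedom), two independent groups give one significant and one non-significant result with probability 2p(1 − p).

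| n per group | S (kg) | p | 2p(1 − p) |
|---|---|---|---|
| 7 | 0.347 | 0.608 | 0.48 |
| 7 | 0.375 | 0.544 | 0.50 |
| 11 | 0.347 | 0.853 | 0.25 |
| 11 | 0.375 | 0.796 | 0.32 |

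**4. Power of the sized contrast.** A two-sample t-test of 0.65 kg with the same S has 84–89% power at 7 completers per group. The stated 50% dropout from 11 leaves 5.5; at 5–6 completers power is 67–83%.

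**5. Multiplicity (lesser point).** The paired-test sentence names 15 items. Calorie intake and macronutrients are intake measures, which leaves 13 body or biomarker outcomes. With no true change and independent outcomes, the chance of at least one p < 0.05 is 1 − 0.95¹³ = 0.487. Simulating one set of 13 equally correlated outcomes (one-sample t on change) gives:

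| Assumed correlation | n = 11 | n = 44 |
|---|---|---|
| 0.5 | 0.355 | 0.34 |
| 0.8 | 0.209 | 0.20 |
| 0.9 | 0.150 | 0.14 |

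The range is roughly 14–36%, with 49% as the figure under independence.

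**The case against.** **The genotype comparison is planned, because it is the stated aim.** This stands as far as it goes. A reader might infer that the investigators did not intend to compare genotypes, but the specific aims say otherwise. What is missing is a test assigned to the aim.

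**Weight is the implied primary outcome.** The sizing supports that reading. Against it, the outcome-indicator sentence leaves weight out, and its only planned test of change is before versus after.

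**The multiplicity figures can be made to look alarming.** A reader might multiply 13 outcomes by four groups and obtain 1 − 0.95⁵² = 93%. The documents do not support that figure. They do not say the tests are run per group, and the outcomes are far from independent: BMI is weight over height squared with adult height effectively fixed over 28 days, and waist-hip ratio is built from two other listed items. A no-change null is not neutral either. Weight loss is expected on the diet, improvement in cardiovascular risk factors is part of the rationale, and controls receive education, guidance and monitoring. Multiplicity is therefore the lesser point.

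**The study is small.** That is a fair reason to treat formal multiplicity control as optional. It does not excuse leaving the aims without a test, and the plan claims 90% power and a fixed threshold.

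**The missing text may contain the test.** This is possible. However, the section headed Statistical analysis is available and runs through to its significance threshold.

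**Conclusion.** The concern holds. In the available text, the contrast named in the aims and used for sizing has no assigned test, and the paired t-tests cannot stand in for it. Judging genotype by which group reaches significance would give discordant results in 48–50% of trials at 7 per group and 25–32% at 11, with no true genotype difference. Those figures rest on an equal true loss of 0.35 kg, independent groups and an SD inferred from n = 7; they illustrate the problem and do not predict the trial's error rate.

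The absence of a primary outcome is also real. Its size, roughly 14–36% for one set of 13 outcomes, depends on assumed correlations and on no outcome truly changing.

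A reader might also infer that the 90% power is wrong. The documents do not show that: without a value for S it can be neither confirmed nor refuted. It refers only to the two-group weight contrast.

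**What to change.** **Needed, in B.9(b):**
- Add a between-group comparison of change for the stated aims: ANCOVA of the endline value on baseline across the four groups, with diet, genotype and diet-by-genotype terms.
- Report the DAC versus DTH contrast on which the trial was sized, and state that it compares genotypes and not randomised arms.
- Name one primary outcome and contrast. Body-weight change, DAC versus DTH, keeps the sizing basis. If the interaction, the randomised diet effect or a cardiovascular indicator is preferred, state that it was not sized.
- Keep the paired t-tests as descriptive within-group results, and say how they are grouped.
- State that the 90% power refers only to the two-group weight contrast, and give the value of S so that it can be checked.

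**Optional:** a multiplicity procedure such as Holm for the three biomarkers.

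**Cost.** Wording only, using data already planned. Data collection was scheduled for November 2023 to February 2024, so if outcomes have been seen, the choice of primary must be labelled post hoc. Some before-after results lose their status as main findings. DAC versus DTH leaves out both control groups. The interaction will be imprecise: it combines four group means where the sized contrast uses two, so its variance is doubled and equal power for the same 0.65 kg would need about twice the completers per group (14 where the formula gives 7).
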